1.3. Schedule of Activities

	Screening	Treatment Period ^a						ET ^b	Follow-Up ^c	Notes
Visit	Screening	Week 0	Week 2	Week 4	Week 6	Week 8	Week 12		Week 16	
Study Day	-42 to Day -1	Day 1	15	29	43	57	85		113	Visit windows post-randomization through Week 12: ± 3 days from the specified study day. Visit window Week 16: 1 week prior/+2 days from the specified study day.
Procedures										
Written Informed Consent	X									Written informed consent may be obtained via telephone in accordance with Section 10.1.2 . Screening may be initiated via telephone.
Patient Fasting	X	X	X	X	X	X	X	X	X	Patients must be in fasted state for at least 8 hours prior to blood collection and study drug administration, where applicable.
Randomization		X								
Review Inclusion and Exclusion Criteria	X	X								Recheck clinical status before randomization and first dose of study drug.
Demographics	X									Includes age, sex, and race/ethnicity.
Height and Weight	X	X	X	X	X	X	X	X	X	Height and weight are collected at Screening and will be used to calculate BMI for eligibility. Waist circumference is also measured at Screening. Only weight is collected on other days indicated.
Medical History	X	X								Includes details of illnesses and allergies, date(s) of onset, whether condition(s) is currently ongoing, and medication history, including alcohol use.

	Screening	Treatment Period ^a						ET ^b	Follow-Up ^c	Notes
Visit	Screening	Week 0	Week 2	Week 4	Week 6	Week 8	Week 12		Week 16	
Study Day	-42 to Day -1	Day 1	15	29	43	57	85		113	Visit windows post-randomization through Week 12: \pm 3 days from the specified study day. Visit window Week 16: 1 week prior/+2 days from the specified study day.
Physical Examination	X	X	X	X	X	X	X	X	X	A complete physical examination will be performed at Screening and Week 16. A targeted physical examination will be performed at all other visits, as needed.
Vital Signs	X	X	X	X	X	X	X	X	X	Includes temperature, pulse rate, respiratory rate, and blood pressure.
Chemistry ^d	X	X	X	X	X	X	X	X	X	Specific analytes are listed in Appendix 1 . ALT and AST stability may be evaluated prior to randomization per Section 5 . Increased monitoring criteria for elevated ALT and/or AST above $2 \times$ Baseline or above $5 \times$ ULN for < 1 week is outlined in Appendix 3 . Refer to Appendix 5 for the eGFR formula, to be calculated by central lab.
Hematology ^d	X	X	X	X	X	X	X	X	X	Specific analytes are listed in Appendix 1 .

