Coagulation ^d	X	X								Specific analytes are listed in Appendix 1 . PT/INR will be tested at Screening, Week 0, and if significant abnormal liver function tests are observed.
Fasting Lipid Profile ^d		X			X		X	X		Specific analytes are listed in Appendix 1 .
Serology	X									Includes HBsAg, anti-HCV, and anti-HIV.

	Screening	Treatment Period ^a						ET ^b	Follow-Up ^c	Notes
Visit	Screening	Week 0	Week 2	Week 4	Week 6	Week 8	Week 12		Week 16	
Study Day	-42 to Day -1	Day 1	15	29	43	57	85		113	Visit windows post-randomization through Week 12: \pm 3 days from the specified study day. Visit window Week 16: 1 week prior/+2 days from the specified study day.
COVID-19 Assessment ^{d,e}	X	X			X		X			Screening and on-study COVID-19 assessments should be conducted in accordance with Appendix 8 .
Serum pregnancy test ^d	X	X		X		X	X	X		WOCBP only.
Serum FSH	X									To confirm postmenopausal status, as outlined in Appendix 7 .
Blood Alcohol Test	X									
Urinalysis ^d	X	X			X		X	X	X	Specific analytes are listed in Appendix 1 . Microscopic examination is required if blood or protein is abnormal.
Urine Drug Screen ^d	X	X		X		X	X	X	X	
Total Urine Collection (PK/PD Sub-Study only)		X			X					Total urine collection from 0-8 hours post dose as specified in Appendix 2 .
Intensive PK and PD Sampling (PK/PD Sub-Study only)		X			X		X			Intensive PK sampling will be performed pre-dose and 0.5, 1, 2, 4, 6, 8 and 24 hours after the first dose of study drug on Week 0/Day 1 and Week 6, and at pre-dose and 0.5, 1, 2, 4, 6, 8, 24, 48 and 72 hours after the last dose of study drug at Week 12. Refer to Appendix 2 for additional detail.

	Screening	Treatment Period ^a						ET ^b	Follow-Up ^c	Notes
Visit	Screening	Week 0	Week 2	Week 4	Week 6	Week 8	Week 12		Week 16	
Study Day	-42 to Day -1	Day 1	15	29	43	57	85		113	Visit windows post-randomization through Week 12: \pm 3 days from the specified study day. Visit window Week 16: 1 week prior/+2 days from the specified study day.
Trough PK and PD Sampling ^d		X	X	X	X	X	X	X		Only one sample will be collected at each visit prior to drug administration on the visit day. Patients discontinuing the study at any time for any reason will have one sample collected at the ET visit. Refer to Appendix 2 for additional detail.
Baseline sVAP-1 ^f		X								
NASH/Fibrosis Biomarkers ^d		X			X		X	X		Includes CK-18 (M30 and M65), PIIINP, TIMP-1, HA, PRO-C3, and C3M.
Inflammation Biomarkers ^d		X	X	X	X	X	X	X		Includes hs-CRP, IL-6, ICAM-1, and VCAM-1.

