Take Study Drug Capsules		←=====→									Patients must be in fasted state for at least 8 hours prior to study drug administration. At all study visits, study drug administration will be observed at the study site. Patients should be instructed to hold their dose of study drug on visit days until all visit procedures have been completed. On all other days, patients will self-administer the study drug orally once daily in the morning on an empty stomach, after an 8 hour fast.

a. If a patient requires home quarantine due to SARS-CoV-2 infection or exposure, or due to COVID-19 symptoms or other associated concern with attending an in-person study visit, home health care visits may be conducted to continue study assessments in the patient's home where feasible, and/or remote visits via telephone, telemedicine, or other appropriate virtual communication may be substituted for a visit to the site.

- b. Patients discontinuing the study at any time for any reason prior to Week 12 (Early Termination) should complete the ET visit as soon as feasible and return for a Follow-Up 4 weeks (-1 week /+2 days) after the last dose of study drug.
- c. The Follow-Up may take place at Week 16 (-1 week /+2 days) or 4 weeks (-1 week /+2 days) after the last dose of study drug if patients discontinue the study at any time for any reason prior to Week 12 (Early Termination).
- d. Samples collected during the treatment period should be collected pre-dose.
- e. In the event of symptoms suggestive of COVID-19, ad hoc testing (including molecular test such as PCR or viral antigen serology, and/or antibody testing), may be completed at Investigator's discretion.
- f. sVAP-1 will be collected along with trough PD sampling.
- g. MRI-PDFF data will be collected along with MRI cT1.
- h. If a patient is required to be quarantined due to active infection of COVID-19 or exposure to COVID-19, or is otherwise unable to visit the site due COVID-19, study drug may be mailed to the patient or made available via another appropriate mechanism (i.e., curbside pickup, etc.). See [Section 6.8.1](#) for additional guidance in the event of hospitalization for COVID-19.

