Appendix 3: Liver Chemistry Increased Monitoring Criteria

[Table 4](#) summarizes requirements for follow-up of liver function test abnormalities.

Table 4 Liver Chemistry Increased Monitoring Criterion and Follow-Up

Criterion	Actions
Elevated ALT and/or AST above 2 × Baseline or above 5 × ULN for < 1 week	
• Patient can continue study drug at the discretion of the Investigator• Repeat measurement of LFTs (including ALT, AST, ALP, and total bilirubin) will be performed within 48-72 hours to confirm the abnormalities and to determine if they are increasing or decreasing. If total bilirubin is increased there should be a reflex to direct and indirect bilirubin.• PT/INR and albumin will be tested when significantly abnormal liver function is observed, and repeated with repeat measurement of LFTs.• Upon confirmation of elevated LFTs, close observation by repeating LFTs every 24 to 72 hours will be initiated immediately.• Frequency of monitoring can be decreased as LFTs decrease at the Investigator's discretion.• The Investigator will collect detailed history information on concomitant symptoms, new medications, drug or alcohol exposure, etc., to identify possible cause of abnormal LFTs.• Close observation on abnormal LFTs will last until the parameters return to baseline, or to a stable level judged by the Investigator.

Note: If one of the following situations occurs and is considered related to the study drug without alternative etiology, study drug may be discontinued at the discretion of the Investigator and the Medical Monitor should be informed (with repeat test performed within 48-72 hours once initial abnormality is detected):
 
• ALT or AST > 8 × ULN• ALT or AST > 5 × ULN for more than 1 week• ALT or AST > 2 × Baseline with the appearance of fatigue, nausea, vomiting, right upper quadrant pain or tenderness, fever, rash, and/or eosinophilia (> 5%)• ALT or AST > 2 × Baseline and total bilirubin > 2 × ULN or INR > 1.5 for more than 1 week, confirmed with a repeat assessment	

Abbreviations: ALP = alkaline phosphatase; ALT = alanine transaminase; AST = aspartate transaminase; INR = international normalized ratio; LFT = liver function test; PT = prothrombin time; ULN = upper limit of normal

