#### **9.3.1. Treatment Emergent Abnormalities**

Quantitative laboratory tests will be assigned grades based on National Cancer Institute Common Terminology Criteria for Adverse Events (NCI CTCAE) Version 5. For each applicable laboratory test, a treatment emergent abnormality will be defined as a post-baseline through Week 16 CTCAE grade worsening of  $\geq 2$  grades.

The number and percentage of patients overall and by laboratory test, with any treatment emergent laboratory abnormality, CTCAE worsening of  $\geq 2$  grades, will be presented.

Listings will be presented for any patient with any treatment emergent laboratory abnormality (any increase in CTCAE grade). Normal ranges provided by the central laboratory will be presented in a listing.

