### 9.3.2. Assessments of Potential Drug Induced Liver Injury

Modified Hy's rule by Bjornsson ([Bjornsson 2005](#)) is defined as patients with ALT or AST values  $>3$  ULN and total bilirubin  $>2$  ULN (based on the same blood draw of ALT, AST, and total bilirubin while on study drug, or within 30 days of last received dose) will be used to assess the potential for study drug-induced liver toxicity. Any patient meeting the criteria will be presented in a by-patient listing.

The criteria for increased laboratory monitoring or consideration for study drug discontinuation on study are specified in protocol appendix 3 and will be included in the analysis dataset and listed.

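### The modified Hy's listing in SAP 9.3.2 stops 30 days after last dose, so an in-window Week 16 panel on day 31-33, or a later repeat, can fall outside it (minor reporting gap)

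*SAP*

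**What the plan says.** SAP 9.3.2 lists patients with ALT or AST above 3 times ULN together with total bilirubin above 2 times ULN. The values must be "based on the same blood draw of ALT, AST, and total bilirubin", and the draw must be made "while on study drug, or within 30 days of last received dose". The same section also lists the Protocol Appendix 3 criteria, with no time limit stated.

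The neighbouring SAP sections use wider windows:
- 9.3.1: "a treatment emergent abnormality will be defined as a post-baseline through Week 16 CTCAE grade worsening" of at least two grades.
- 9.3.3: grade shifts run from baseline to the worst post-baseline value, with no end day stated.
- 9.2: adverse events count to 30 days after last dose or through Week 16, and related SAEs count even after that.

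Timing comes from the Protocol, Section 1.3:
- For Week 12: "Visit windows post-randomization through Week 12: ± 3 days from the specified study day".
- For follow-up of completers: "Visit window Week 16: 1 week prior/+2 days from the specified study day".
- For early terminators: "4 weeks (-1 week /+2 days) after the last dose of study drug if patients discontinue the study".

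Protocol Appendix 3 asks for repeat liver tests, bilirubin included, 48-72 hours after a qualifying elevation. It continues: "Upon confirmation of elevated LFTs, close observation by repeating LFTs every 24 to 72 hours will be initiated immediately". Those repeats go on until values return to baseline or stabilise.

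**The concern.** The 30-day limit and the Week 16 window are measured from different starting points. The limit runs from the last dose. For completers the Week 16 window is fixed to Day 113, whatever day Week 12 took place. An early Week 12 visit therefore lengthens the gap, and a panel drawn fully within the visit windows can fall beyond the limit. Repeat tests prompted by a Week 16 abnormality come later still.

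Both limits must be met on one draw. A patient whose bilirubin crosses only on a draw after day 30 is therefore not listed. SAP 9.3.2 is where the plan assesses potential drug-induced liver injury, safety is the primary objective, and the trial has about 80 patients. One unlisted case would matter to a reader of that listing. The SAP gives no reason for a window narrower than those beside it.

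**Working it through.** **Inputs**
- Cut-off: 30 days after last dose (SAP 9.3.2).
- Week 12: Day 85 ± 3, so Day 82-88 (7 days).
- Week 16: Day 113, -7/+2, so Day 106-115 (10 days).
- Last dose of completers: at the Week 12 visit. Section 1.3 implies this for the PK/PD sub-study ("72 hours after the last dose of study drug at Week 12"). It is assumed for other patients; Protocol 6.5 has dosing observed at every study visit.
- First repeat: +2 to +3 days. Each further repeat: +1 to +3 days (Protocol Appendix 3).

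**The plan's own figure.** 113 - 85 = 28 days = 4 weeks, which agrees with the stated 4-week Follow-up Period.

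**Range for the Week 16 panel.** Shortest gap: 106 - 88 = 18 days. Longest gap: 115 - 82 = 33 days, which is 28 + 2 + 3.

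**Pairs past day 30.** There are 7 × 10 = 70 pairs. Week 16 day minus Week 12 day exceeds 30 for:
- Day 82 with Day 113, 114 or 115 (31, 32, 33 days)
- Day 83 with Day 114 or 115 (31, 32 days)
- Day 84 with Day 115 (31 days)

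That is 3 + 2 + 1 = 6 pairs, or 8.6%. With Week 12 on Day 85 the range is 21-30 days, so none exceeds 30.

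**Adding the repeats**

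| Draw | Days after Week 16 | Past day 30, all pairs | Past day 30, Week 12 on Day 85 | Days since last dose, both visits on target |
|---|---|---|---|---|
| Week 16 panel | 0 | 6/70 | 0/10 | 28 |
| First repeat | 2 to 3 | 15/70 to 21/70 (21-30%) | 2/10 to 3/10 | 30 to 31 |
| Second repeat | 3 to 6 | 21/70 to 42/70 (30-60%) | 3/10 to 6/10 | 31 to 34 |
| Third repeat | 4 to 9 | 28/70 to 60/70 (40-86%) | 4/10 to 9/10 | 32 to 37 |

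With both visits on target, a first repeat at 48 hours is on day 30 and is included. At 72 hours it is on day 31 and is not. Every later repeat is past day 30.

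**Early terminators.** Follow-up is 28 days after last dose, -7/+2, so 21-30 days. An in-window follow-up panel is always covered; only repeats can fall outside.

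**Sensitivity.** If the last dose is the day before Week 12, or if days are counted with the +1 rule of SAP 4.5, the longest gap is 34 days and 10 of 70 pairs exceed 30. With Week 12 on Day 85, one pair then exceeds 30 (115 - 85 + 1 = 31). SAP 9.3.2 does not say how its 30 days are counted.

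**Whether other outputs apply the same rule.** The Appendix 3 combined criterion needs ALT or AST above 2 times Baseline, and Protocol exclusion 4 admits patients with values up to 5 times ULN. As an illustration, a patient with baseline ALT at 2 times ULN rises to 3.5 times ULN, with bilirubin above 2 times ULN. ALT is then 3.5 / 2 = 1.75 times Baseline: above the Hy's limit of 3 times ULN, but below the Appendix 3 limit. SAP 9.3.1 and 9.3.3 grade each test separately.

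**The case against.** The case for leaving the rule alone has weight.

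- **Thirty days is a coherent choice.** It equals the 28-day follow-up target plus its 2-day allowance, and it also appears in the adverse event definition. This explains the limit, but it holds only where follow-up is timed from the last dose. For completers it is timed from Day 113.
- **The values are not lost.** SAP 9.3 lists all safety laboratory data by patient. SAP 9.3.1 lists any increase in CTCAE grade, 9.3.3 uses the worst post-baseline value, and 9.3.2 lists the Appendix 3 criteria. This stands. However, none of these applies the Hy's rule itself, so a reader would have to find the case unaided.
- **SAP 9.3.1 supports only part of the change.** It ends at Week 16, so on its own it argues for covering days 31-33, not later repeats. This also stands. Support for repeats comes from 9.3.3 and from the fact that Appendix 3 already collects them.

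A reader might infer three stronger points that the documents do not support:
- **That most repeat tests are excluded.** The first repeat is past day 30 in only 21-30% of pairs. Larger shares apply to later repeats.
- **That off-drug cases in general are left out.** The first 30 off-drug days are covered. A patient who meets both limits by day 30 is listed whatever later repeats show.
- **That irreversible inhibition makes late liver injury likely.** Irreversibility describes the drug's action on its target. Protocol 2.2.2 reports rapid clearance from plasma, and nothing readable in the documents links the drug to delayed liver injury.

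**Conclusion.** The point holds as a minor reporting gap. The missed case is specific: a patient who first meets both limits on a Week 16 panel on day 31-33, or on a repeat after day 30. Such a patient is missing from the modified Hy's listing, not from the report.

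The exposure is 6 of 70 day pairs for the Week 16 panel and 15 to 21 of 70 for the first repeat. With both visits on target, it also includes every repeat after the first. The counts give each pair equal weight, take the last dose at Week 12 and use plain day differences. They are not visit probabilities. They also say nothing about how often a patient would first cross both limits about four weeks off drug; the documents give no rate for that, and it is probably low. Sample size, error rates and the other safety summaries are unaffected.

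A reader might infer a larger gap for patients who stop drug early but keep the study-day visit schedule. The Protocol does not state clearly that they do, so no such claim is made here.

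**What to change.** In SAP 9.3.2, apply the modified Hy's rule to all post-baseline draws through the Week 16/Follow-Up visit, including any later unscheduled repeat draws. Print days since last dose for each listed draw, flag draws more than 30 days after last dose, and state how the days are counted.

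This covers all 70 of 70 in-window Week 16 pairs, against 64 of 70 now, and every repeat. It costs one phrase, one listing column and a flag, and needs no new data. The downside is that an occasional off-drug case of other cause may be listed; the printed interval lets a reader judge it.

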### 9.3.3. Shifts in CTCAE Grade

Quantitative laboratory tests will be assigned grades based on National Cancer Institute Common Terminology Criteria for Adverse Events (NCI CTCAE) Version 5. Shifts in CTCAE grade of laboratory tests will be presented from baseline to worst post-baseline value. Summaries will present the number and percentage of patients with shifts in laboratory grade by treatment group. Denominators for percentages will be the number of patients with non-missing data at the specific assessment and baseline.

Some lab tests include additional clinical criteria which cannot be determined programmatically. [Table 10](#) below specifies the grade with clinical criteria in italics. The text in italics will not be considered when assigning grades programmatically.

**Table 10: CTCAE Laboratory Tests with Clinical Criteria**

Bicarbonate (Blood bicarbonate decreased):

Grade 1: <LLN and no intervention initiated.

Prothrombin Time (PT)/International Normalized Ratio (INR) (INR increased):

Grade 1: >1.2 - 1.5; >1 - 1.5 x baseline if on anticoagulation; monitoring only indicated

Grade 2: >1.5 - 2.5; >1.5 - 2.5 x baseline if on anticoagulation; dose adjustment indicated

Grade 3: >2.5; >2.5 x baseline if on anticoagulation; bleeding

eGFR (Chronic Kidney Disease):

Grade 4: <15 ml/min/1.73m^2; dialysis or renal transplant indicated

Glucose (Hypoglycemia):

Grade 4: <30 mg/dL; <1.7 mmol/L; life-threatening consequences; seizures.

Potassium (Hypokalemia)

• Grade 2: Symptomatic with <LLN - 3.0 mmol/L; intervention indicated

• Grade 3: <3.0 - 2.5 mmol/L; hospitalization indicated

• Grade 4: <2.5 mmol/L; life-threatening consequences

Potassium (Hyperkalemia)

• Grade 2: >5.5 - 6.0 mmol/L; intervention initiated

• Grade 3: >6.0 - 7.0 mmol/L; hospitalization indicated

• Grade 4: >7.0 mmol/L; life-threatening consequences

Sodium (Hyponatremia)

• Grade 2: 125-129 mmol/L and asymptomatic

• Grade 3: 125-129 mmol/L symptomatic; 120-124 mmol/L regardless of symptoms

• Grade 4: <120 mmol/L; life-threatening consequences

Sodium (Hypernatremia)

• Grade 2: >150 - 155 mmol/L; intervention initiated

• Grade 3: >155 - 160 mmol/L; hospitalization indicated

• Grade 4: >160 mmol/L; life-threatening consequences

Albumin (Hypoalbuminemia)

• Grade 4: Life-threatening consequences; urgent intervention indicated.

#### 9.3.4. COVID-19

SARS-CoV-2 test for active infection and SARS-CoV-2 antibody test results, using central and local labs, will be presented in by-patient listings. A separate listing for central and local laboratory normal ranges by lab test, lab parameter, sex, and age will be presented.

#### 9.4. Vital Signs

Temperature, pulse rate, respiratory rate, and blood pressure will be assessed and maintained in source documentation, not reported in the EDC, and therefore will not be included in analyses. Any clinically significant abnormalities will be reported as adverse events.

#### 9.5. Electrocardiograms

The investigator interpretation is collected as normal, abnormal not clinically significant (NCS), or abnormal clinically significant (CS). Patients whose interpretation shifts from normal to abnormal (CS or NCS) will be listed separately including description of the abnormality and any associated comments.

All ECG results will be presented in by-patient data listings. If applicable, cardiologist consult information will be presented in a separate by-patient data listing.

## **10. OTHER ASSESSMENTS**

Other assessments will be provided in by-patient data listings only; no summary tables will be provided, including but not limited to the following:

- Eligibility details including unmet eligibility criteria
- Informed consent and re-consents
- Randomization schema
- Alcohol use
- Physical examination collection information
- Serology
- Pregnancy testing
- FSH test
- Urine drug screen
- Alcohol test
- Urinalysis and Urine Microscopic Examination
- Cardiology consult
- Overdose
- Comments

